Transient acantholytic dermatosis (Grover's disease) is a rare skin disorder that presents most commonly as small, pruritic, erythematous papules on the trunk, particularly the central chest and back in males older than forty or fifty. The etiology is largely unknown, but the disease is thought to be associated with sweating and heat. The time course of Grover's disease is variable: some patients present with a self-limited two to four week eruption or a persistent non-resolving pattern. A clinical diagnosis can be made, but it is often confirmed through skin biopsy demonstrating typical features.¹

Psoriasis vulgaris is a common chronic inflammatory skin disorder that presents as erythematous, well-demarcated plaques with overlying silvery scale. It is associated numerous co-morbidities including obesity, cardiovascular disease, and autoimmune disease. Psoriasis is caused by the complex interactions of numerous inflammatory cells (T-cells and dendritic cells) and cytokines (TNF-alpha, Il-23, Il-12) that leads to abnormal differentiation in the epidermis, vascular dilation, and inflammatory cell recruitment.²

Blue light therapy in psoriasis has been studied in 2 randomized clinical trials, which have shown improvement in erythema and the LPSI score before and after therapy³⁻⁴. Although these studies studied the clinical response of psoriasis to blue light, neither examined histopathological or serological evidence of the immune system after blue light therapy. This study will also control for confounding variables such as 10% salicylic petroleum gel and moisturizers that were used in these two studies.

Standard of care treatment for Grover's disease include high potency topical steroids, application moisturizers, or emollients. Grover's disease patients may also minimize symptoms by avoiding triggers such as sweating or heat.

Standard of care for psoriasis include use of emollients, topical steroids, topical vitamin D, tar, calcineurin inhibitors, UV light phototherapy, and systemic therapies include methotrexate, retinoids, and biologic agents.

STUDY ENDPOINTS:

Objective 1 endpoint

- Recruitment of at least n=10 individuals with Grover's disease
- Recruitment of at least n=10 individuals with psoriasis vulgaris
- Demonstrate device safety as evidenced by absence of adverse events

STU#: STU00210472

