After informed consent a patient will be scheduled to start the study sessions immediately (if not on medications) or after a period of two weeks without using medications related to their skin condition. A site on the body will be identified for treatment with Blue Light, this will be the same site treated throughout the study.

The study visits will take approximately 30 minutes and will be done three times a week (at least 23 hours apart) over five weeks (15 visits total). Each session will consist of 16

STU#: STU00210472

minutes of Blue Light phototherapy with the BLU-U device over the affected area. Before starting the first, seventh and after the last session the patient will have a single, 6mm, punch biopsy of a characteristic lesion on the treated side only and a blood draw not exceeding 30 cc or two tablespoons in a visit. Tissue and blood, samples will be collected under the Dermatology Tissue Acquisition and Biorepository (IRB# STU00009443) protocol upon completion of the consent form for STU00009443.

During the first and last study visit the patient will be asked to complete surveys relating to their comfort and experience with the phototherapy symptoms and psychometric surveys of skin-related symptoms and skin-related quality of life.

In addition photographs will be taken of the afflicted areas before the first treatment, on the first visit, third visit after every 3 treatments until the end of the study as outlined in the table below.

Procedure Table

	Blue Light Phototherapy	Biopsy of lesional treated area	Blood Draw	Psychometric and Skin QoL survey	Photographs of afflicted skin area
Visit 0 - Consent					X
Visit 1 - Baseline	X	X	X	X	X
Visit 2	X				
Visit 3	X				X
Visit 4	X				
Visit 5	X				
Visit 6	X				X
Visit 7	X	X	X		
Visit 8	X				
Visit 9	X				X
Visit 10	X				
Visit 11	X				
Visit 12	X				X
Visit 13	X				
Visit 14	X				
Visit 15	X	X	X	X	X
Early completion (If condition resolved before final visit)	X	X	X	X	X

In this single arm, prospective clinical trial patients with Grover’s disease (n=10) will be invited to participate. A baseline biopsy of a characteristic lesion will be performed. Patients will be asked to complete a baseline psychometric survey of skin-related

STU#: STU00210472

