symptoms and skin-related quality of life. Patients will then be asked to present to the phototherapy unit at Northwestern Dermatology for 15 total sessions of blue light therapy divided into 3 sessions a week for 5 weeks. The target irradiance is 14 mW/cm² with a total dose of 9 J/cm² requiring ~16 min per treatment. At each treatment session, clinical photos will be taken along with blue-light dosimeter readings at various locations of the body. At the mid-point of the study (7 sessions), an additional biopsy will be taken of a characteristic lesion. At the end-point of the study (15 sessions), a final biopsy will be taken of a characteristic lesion. If the lesion(s) is/are resolved a biopsy will be done adjacent to a previous biopsy. Patients will be asked to complete psychometric surveys relating to their comfort and experience with the phototherapy symptoms. In addition, they will complete psychometric surveys of skin-related symptoms and skin-related quality of life to compare against baseline. Subjects on the therapy will be asked to refrain from using systemic treatments throughout the trial with a 2-week washout period before the start of the trial. Topical treatments may be used, except in the area that is identified for treatment with Blue Light phototherapy provided by this study.

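### The stated irradiance, session time and light dose cannot all be right: 14 mW/cm² for 16 minutes gives 13.44 J/cm², not 9 J/cm²

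*Combined protocol and SAP*

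**What the plan says.** The dose is specified under Procedures Involved, in the paragraphs for the two cohorts. Both contain the same sentence: "The target irradiance is 14 mW/cm² with a total dose of 9 J/cm² requiring ~16 min per treatment". The Grover's paragraph sets the course at "15 total sessions of blue light therapy divided into 3 sessions a week for 5 weeks"; the psoriasis paragraph also has 15 sessions.

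The general description of the study visits, earlier in the same section, gives the time again without an approximation sign: "Each session will consist of 16" (the sentence runs over a page break to the word minutes). It also fixes a single treated area: "A site on the body will be identified for treatment with Blue Light, this will be the same site treated throughout the study".

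Dosimetry is planned in both cohort paragraphs: "At each treatment session, clinical photos will be taken along with blue-light dosimeter readings at various locations of the body". Nothing says how a reading alters the exposure, or that delivered dose is calculated or reported.

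**The concern.** The three quantities are tied by a physical identity: energy per unit area equals power per unit area multiplied by time. Two of them fix the third. The protocol states all three, and they do not agree.

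The two descriptions also treat time differently. In the cohort paragraphs the time is what the dose requires, so it follows from dose and irradiance. In the visit description it is a fixed instruction. No text says which prevails.

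At stake is the exposure to which every result will be attached. The endpoints include device safety ("Demonstrate device safety as evidenced by absence of adverse events"), preliminary efficacy, and T-cell and keratinocyte findings in serial biopsies. Both cohorts are single-arm with 10 patients each, so no comparator arm at another dose would show what a different dose does. If 14 mW/cm² for 16 minutes is what patients actually receive, anyone who repeats the regimen from the stated 9 J/cm² would deliver a third less light (1 − 9/13.44 = 33%).

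**Working it through.** **Inputs** (Procedures Involved, same for both cohorts): irradiance 14 mW/cm² = 0.014 W/cm²; time 16 min = 960 s; dose 9 J/cm²; 15 sessions.

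**Formula:** dose (J/cm²) = irradiance (W/cm²) × time (s).

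**Attempt to reproduce the stated dose:** 0.014 × 960 = 13.44 J/cm². The stated figure is 9; 13.44/9 = 1.493, or +49%. It is not reproduced.

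**Solving for each figure in turn:**

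| Figures kept | Figure that must change | Result |
|---|---|---|
| 14 mW/cm², 16 min | dose | 0.014 × 960 = 13.44 J/cm² |
| 14 mW/cm², 9 J/cm² | time | 9/0.014 = 643 s = 10.7 min (16 − 10.7 = 5.3 min shorter) |
| 9 J/cm², 16 min | irradiance | 9/960 = 0.009375 W/cm², about 9.4 mW/cm² (1 − 9.375/14 = 33% below target) |

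**Can rounding explain it?** Move every figure to the edge of its rounding interval in the plan's favour: 0.0135 × 930 s = 12.56 J/cm² against 9.5, still 32% too high (12.56/9.5 = 1.32). Stretching the approximate time to 15 minutes gives 0.0135 × 900 s = 12.15 J/cm², still 28% too high (12.15/9.5 = 1.28). Rounding does not explain it.

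**Can the dose be a total for the course?** 9/15 = 0.6 J/cm² per session, which takes 0.6/0.014 = 43 s. That is further from 16 minutes, not closer.

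**Cumulative dose if 14 mW/cm² is delivered for 16 minutes:**

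| Point | At 13.44 J/cm² per session | At 9 J/cm² per session |
|---|---|---|
| Mid-study biopsy, 6 sessions given | 6 × 13.44 = 80.6 | 6 × 9 = 54 |
| Mid-study biopsy, 7 sessions given | 7 × 13.44 = 94.1 | 7 × 9 = 63 |
| End, 15 sessions | 15 × 13.44 = 201.6 | 15 × 9 = 135 |

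Two mid-study rows are shown because the visit description places that biopsy before the seventh session, while the cohort paragraphs can be read as placing it after seven.

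**Range for a 16-minute session.** Irradiance at the skin is an assumption here; the documents give only the target.

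| Skin irradiance | Delivered dose | Against 9 J/cm² |
|---|---|---|
| 9.4 mW/cm² | 9.0 J/cm² | 0% |
| 12 mW/cm² | 0.012 × 960 = 11.5 J/cm² | +28% |
| 14 mW/cm² | 13.44 J/cm² | +49% |

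**The case against.** The strongest reply is that staff know what to do. Device, session length and number of sessions agree wherever they appear, and no text tells anyone to stop at 9 J/cm². Read this way, the regimen is a fixed 16 minutes with a mis-stated dose or irradiance beside it. All patients are assigned the same session, no listed endpoint uses J/cm², and no analysis, dose limit or sample size depends on it. Before-and-after comparisons within patients would not change as long as the session stays at 16 minutes. The 14 mW/cm² is a target, so the 49% is conditional, and dosimeter readings at every session could help recover the true dose.

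Much of this stands. Device, time and session count are defined, the 49% applies only if the target is met, and no harm from 13.44 J/cm² is shown or claimed. None of it makes the sentence correct. If time governs, the stated dose is wrong whenever the target irradiance is achieved. If dose governs, the 16-minute instruction overexposes by 5.3 minutes per session at target. The plan does not choose between the two.

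The dosimetry helps only in part. Readings across the body do not exclude the treated site, but they do not commit to it either, and nothing requires a delivered dose to be derived from them.

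**Conclusion.** The concern holds. The dose sentence is arithmetically impossible as written, for all 20 planned patients. The mismatch is 13.44 against 9 J/cm² per session (+49%) and 201.6 against 135 J/cm² over the course, on the assumption that 14 mW/cm² reaches the skin for the full 16 minutes. It falls to zero if the actual irradiance is about 9.4 mW/cm². The inconsistency itself needs no assumption beyond the definition of dose. The documents do not reveal which figure is wrong. Because this is the dose of the only intervention, it should be settled before patients are treated.

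**What to change.** 1. Correct whichever figure is wrong, so that irradiance × time = dose in both cohort paragraphs. The consistent sets are 14 mW/cm², 16 min, 13.44 J/cm²; or 14 mW/cm², 10.7 min, 9 J/cm²; or 9.4 mW/cm², 16 min, 9 J/cm². The visit description needs editing only if the time changes.
2. Label the figure as dose per session, and give the 15-session total separately if it is wanted.
3. State whether time or J/cm² governs when a dosimeter reading differs from target.
4. Specify that one of the planned readings is taken at the treated site, and report delivered dose for each patient, per session and cumulatively.

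If dose or irradiance is the wrong figure, item 1 is a wording correction. If time is wrong, each session becomes 5.3 minutes shorter, which is a change to treatment and not only to text. Items 2 and 3 are wording. Item 4 uses dosimetry already planned for every session; what it adds is a named location for one reading and the reporting of delivered dose.

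### In both cohorts the stated irradiance, dose and session time cannot all be true: 14 mW/cm² for 16 minutes gives 13.4 J/cm², not 9 J/cm²

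*Combined protocol and SAP*

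**What the plan says.** The Procedures Involved section of the combined protocol and SAP defines the light exposure in three places.

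- The paragraph on the Grover's cohort: "The target irradiance is 14 mW/cm² with a total dose of 9 J/cm² requiring ~16 min per treatment".
- The paragraph on the psoriasis cohort, which repeats that sentence with the same three figures.
- The general description of study visits: "Each session will consist of 16" (the sentence continues with minutes of blue light from the BLU-U device), here without an approximation sign.

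The course is "15 total sessions of blue light therapy divided into 3 sessions a week for 5 weeks" in the Grover's paragraph, and 15 sessions at three per week in the psoriasis paragraph too. One treatment site is chosen per patient: "A site on the body will be identified for treatment with Blue Light, this will be the same site treated throughout the study".

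Both cohort paragraphs also plan measurements: "At each treatment session, clinical photos will be taken along with blue-light dosimeter readings at various locations of the body". The section does not say which of irradiance, dose and time governs, and it gives no rule for adjusting session time to a measured irradiance.

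**The concern.** Any two of irradiance, dose and time fix the third. The sentence presents the session time as what the stated dose requires at the stated irradiance, but the three figures do not fit together, and the same mismatch stands in both cohorts.

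The light dose defines the intervention. Both cohorts are single-arm, so there is no comparator within the trial; the results describe what happened at whatever exposure was given. If the lamp delivers 14 mW/cm² and staff time 16 minutes, patients receive about half as much light again as the protocol records. A later study that adopted 9 J/cm² from this protocol would then give a third less light per session than these patients had.

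Staff also lack a single consistent instruction. Timing by the clock gives 16 minutes, while dosing to 9 J/cm² at 14 mW/cm² gives under 11. Both fit within the planned 30-minute visit, so the schedule would not expose the discrepancy.

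**Working it through.** **Inputs** (all from Procedures Involved)

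- Irradiance: 14 mW/cm² = 0.014 W/cm² (both cohort paragraphs)
- Dose: 9 J/cm² (both cohort paragraphs)
- Time: 16 min = 960 s (both cohort paragraphs, and the general visit description)
- Sessions: 15

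**Formula:** dose (J/cm²) = irradiance (W/cm²) × time (s)

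**1. Attempt to reproduce the stated dose.** 0.014 × 960 = 13.44 J/cm². The stated 9 is not reproduced. 13.44 / 9 = 1.49, so the computed dose is 49% higher; conversely 9 / 13.44 = 0.67, so 9 is 33% below it.

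**2. Could rounding explain it?**

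- Lowest: 0.0135 × 930 s (15.5 min) = 12.56 J/cm²
- Highest: 0.0145 × 990 s (16.5 min) = 14.36 J/cm²
- A dose reported as 9 could be at most 9.5. The lowest product is still 32% above that (12.56 / 9.5 = 1.32).

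**3. Could a loose approximation of time explain it?** At 14 mW/cm², 14 min gives 0.014 × 840 = 11.8 J/cm² and 18 min gives 0.014 × 1,080 = 15.1 J/cm². Neither is close to 9.

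**4. Could 9 J/cm² be the total for the whole course?** 9 / 15 = 0.6 J/cm² per session, and 0.6 / 0.014 = 43 s. That contradicts 16 minutes.

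**5. Consistent sets.** Keeping two figures and solving for the third:

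| Figures kept | Third figure becomes | Course dose (15 sessions) |
|---|---|---|
| 14 mW/cm² and 16 min | 13.44 J/cm² per session | 15 × 13.44 = 201.6 J/cm² |
| 14 mW/cm² and 9 J/cm² | 9 / 0.014 = 643 s = 10.7 min | 15 × 9 = 135 J/cm² |
| 16 min and 9 J/cm² | 9 / 960 = 0.0094 W/cm² = 9.4 mW/cm² (33% below the stated target) | 15 × 9 = 135 J/cm² |

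**The case against.** The arithmetic is not in dispute; the case on the other side is about consequence and the size of the fix.

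- **No endpoint uses the dose.** Study Endpoints lists recruitment, adverse events, photographs, the DLQI, histopathology, user experience and T-cell and serum markers. No dose-response analysis is planned, and both cohorts carry the same figures, so the discrepancy does not differ between them. This stands as far as it goes: that results will be reported against the dose is an inference, not protocol text. But a single-arm result still needs a correct description of the treatment.
- **The working instruction is clear.** The device is named and the session is 16 minutes. If staff follow the clock, every session has the same timed exposure, and if the time is right, the error is one of description. That is fair, but the documents cannot show that the time is the correct figure.
- **The 49% is conditional.** The protocol calls 14 mW/cm² a target and does not give the delivered irradiance. If about 9.4 mW/cm² reaches the skin, 9 J/cm² in 16 minutes is right and nobody receives an excess. This stands. Even then, the stated irradiance is wrong.
- **Dosimetry is already planned.** Readings are to be taken at every session, so actual exposure may be recoverable. The wording does not exclude the treated site. It does not require a reading there either, and nothing links a reading to the session time.
- **The remedy exceeds the defect.** Correcting the sentence needs only a lamp check and one figure. Recording and reporting dose per session goes further, and is good practice rather than part of the correction. It is cheap because the readings are planned anyway.

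**Conclusion.** The concern holds. In both cohorts the three exposure figures are mutually inconsistent, and neither rounding, a generous reading of the approximate time, nor a whole-course reading of the dose reconciles them. The identical wording in two paragraphs, with the 16 minutes confirmed in a third place, makes a text-extraction fault unlikely.

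The gap is 9 versus 13.4 J/cm² per session (12.6 to 14.4 allowing for rounding), or 135 versus 202 J/cm² over 15 sessions. It describes what patients actually receive only if 14 mW/cm² and 16 minutes are the true settings. The documents do not establish this, and they do not show which figure is wrong. The finding is of an error in how the intervention is specified, not of overdosing or harm. It is minor in severity and easily corrected before treatment starts.

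**What to change.** Before the first treatment, measure the lamp output at treatment distance. Then correct whichever figure is wrong, in both cohort paragraphs and, if it is the time, in the general visit description:

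- if 14 mW/cm² and 16 min stand, state 13.4 J/cm² per session (202 J/cm² over 15 sessions);
- if 14 mW/cm² and 9 J/cm² stand, shorten sessions to 10.7 min;
- if 16 min and 9 J/cm² stand, state 9.4 mW/cm².

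Say which parameter governs, and call the figure dose per session rather than total dose. Keep the planned dosimeter readings and specify that they include one at the skin surface of the treated site. Report measured dose per session and cumulative dose per patient beside the outcomes.

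The cost is one lamp measurement, a text correction, one recorded value per session (at most 15 × 20 = 300 in all) and a short dose table. No patients, visits or patient procedures are added, and no planned reading is lost.

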- Demonstrate preliminary skin efficacy as demonstrated by clinical photo evaluation, patient reported outcomes with Dermatology Life Quality Index (DLQI) and skin histopathology with both Grover's disease and psoriasis vulgaris.
- Obtain user comfort and experience with phototherapy system using psychometric survey.

Objective 2 endpoint

- Elucidate keratinocyte and skin T-cell expression, and viability with blue light phototherapy
- Elucidate changes in circulatory T-cells based on flow cytometry and serum cytokines with blue light therapy.

STUDY INTERVENTION(S) / INVESTIGATIONAL AGENT(S):

The DUSA BLU-U (Model 4170) is a Blue Light Photodynamic Therapy Illuminator is intended to provide phototherapeutic light to the body. Blue light therapy is indicated for dermatological conditions such as actinic keratosis (AK) or inflammatory acne vulgaris. The BLU-U is approved by the FDA (K031805) as a Class II medical device. The BLU-U Illuminator to be used in this study is owned by the Northwestern Memorial Hospital Department of Dermatology and stored at the Dermatology Clinic in Chicago.

PROCEDURES INVOLVED:

Patients with Grover's Disease or Psoriasis vulgaris will be enrolled on the study.

In the informed consent process a Dermatologist will discuss Standard of Care treatment options for Grover's Disease or psoriasis vulgaris. If the patient wishes not to participate in this study the SOC treatment will be available to them. If the patient chooses to participate in this study, they may elect to do SOC treatment at any time (ending participation early) or after the phototherapy study visits are complete. Patients receiving SOC phototherapy (other light type, with activator creams, etc) may participate in this study by blocking a small site from their SOC phototherapy which will be treated with the Blue Light therapy in this trial. The Department of Dermatology has standard of care procedures for blocking specific sites during SOC phototherapy. These procedures will be followed if a patient that is enrolled on the study is simultaneously receiving SOC phototherapy for their condition. The clinical research team will consult with the phototherapy team for any patient that is receiving phototherapy.

No procedures in this study are standard of care for Grover's Disease or psoriasis vulgaris. If the symptoms of resolve before all phototherapy sessions are completed, the patient will have their final assessment and will have completed the study.

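### The treated site is fixed, but the lesions for the mid and final biopsies are not assigned in advance, and only the Grover's cohort has a rule for resolved lesions, so later samples could depend on response

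*Combined protocol and SAP*

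**What the plan says.** Under Procedures Involved, the treated location is fixed: "A site on the body will be identified for treatment with Blue Light, this will be the same site treated throughout the study". The biopsy rule in the same section is: "Before starting the first, seventh and after the last session the patient will have a single, 6mm, punch biopsy of a characteristic lesion". It confines the punch to the treated side but does not identify the lesion.

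Both cohort paragraphs repeat the general term at each time point. At mid-point, for example: "At the mid-point of the study (7 sessions), an additional biopsy will be taken of a characteristic lesion". No section names an index lesion, a baseline map, an order of sampling or the person who chooses.

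Resolution is handled in three places:

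- The Grover's paragraph adds: "If the lesion(s) is/are resolved a biopsy will be done adjacent to a previous biopsy". It does not say which previous biopsy, at what distance, or whether one or all lesions must have cleared.
- The psoriasis paragraph, otherwise parallel, has no equivalent sentence.
- If symptoms "resolve before all phototherapy sessions are completed, the patient will have their final assessment and will have completed the study". For that early-completion visit the procedure table ticks the column headed "Biopsy of lesional treated area", with no location and no distinction between cohorts.

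The samples supply the T-cell counts at baseline, mid-point and completion of 15 sessions (Objective 2). They also supply the histopathology listed as preliminary efficacy evidence under the Objective 1 endpoint.

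**The concern.** Histology is read as change within a patient across three punches, with 10 patients per disease and no control arm. Such a comparison is sound only if the choice of tissue does not depend on how that tissue responded. A clinician asked on the day for a characteristic lesion would naturally take one that still looks like the disease, so cleared lesions would drop out and a real fall in T-cells could be hidden.

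The adjacent rule can work differently. The Background section describes Grover's lesions as small papules, so tissue beside an earlier 6 mm punch may never have been lesional, or may be healing from that punch. Counts there could differ from baseline for reasons unrelated to light.

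In psoriasis, clinicians facing a resolved site would each have to improvise a location. Later analysis cannot recover a lesion that was not sampled.

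**Working it through.** **Planned biopsies.** There are three per patient (section text and procedure table) and 10 + 10 = 20 patients (Study Endpoints). The compensation section agrees with three biopsy visits out of 15: 3 × $50 + 12 × $25 = $450, the stated total. Planned biopsies are 3 × 20 = 60, of which mid and final make 2 × 20 = 40. The 40 is an upper limit on those that could be chosen after light has begun.

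**Mechanism 1, understatement (assumed inputs).** Let the site hold m lesions, each resolving independently with probability p. A lesion assigned beforehand is resolved at the later biopsy with probability p. If a remaining characteristic lesion is taken whenever one exists, resolved skin is sampled only when all have cleared, with probability p^m.

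| p | m = 1 | m = 3 | m = 5 |
|---|---|---|---|
| 0.25 | 0.25 | 0.016 | 0.001 |
| 0.50 | 0.50 | 0.125 | 0.031 |
| 0.75 | 0.75 | 0.42 | 0.24 |

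With one lesion the selection disappears.

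**Mechanism 2, overstatement (assumed inputs).** Suppose no true change, 10 patients and within-patient correlation 0.5. The most marked of m lesions is taken at baseline and an unselected spot later. For m = 3 the expected maximum of three standard normal values is 3/(2√π) = 0.846, so the spurious fall is √0.5 × 0.846 = 0.60 SD. Simulation (20,000 runs) gives 0.40, 0.60 and 0.82 SD for m = 2, 3 and 5. A two-sided 5% paired t-test rejects in 23%, 48% and 78% of runs. With the same selection rule at both times it rejects in about 5%.

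These figures show that either direction is possible. They do not estimate bias in this trial: the documents give no between-lesion variation, no resolution rate and no planned test on histology.

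**Sessions received.** A mid biopsy taken before session 7 follows 6 sessions and leaves 15 − 6 = 9. The cohort paragraphs' 7 sessions, if read as completed, leave 15 − 7 = 8. A patient who resolves before Visit 7 gives 2 samples, not 3. Any early completer's last sample follows fewer than 15 sessions, and the plan does not say whether it joins the 15-session count.

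**Time since light.** Sessions are at least 23 hours apart, so a biopsy before session 7 is at least 23 hours after light (3 days on an assumed Monday/Wednesday/Friday schedule). The table places the last session and the final biopsy both at Visit 15. With visits of about 30 minutes and 16 minutes of light, that interval is about 30 − 16 = 14 minutes at most if the visit keeps to its nominal length.

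**The case against.** A reader might infer that the lesion is picked afresh at each biopsy visit, so that 40 biopsies are in fact selected after treatment begins. The documents do not support that. No section says when, how or by whom the lesion is chosen; they show only that nothing fixes it beforehand. Tissue is also collected under the biorepository protocol (STU00009443), which is not available and may contain a selection or site rule.

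Selection needs several lesions. The protocol treats one site and allows "blocking a small site from their SOC phototherapy which will be treated with the Blue Light therapy in this trial". A single psoriasis plaque leaves only the punch position to choose, so the two diseases are not equally exposed.

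The adjacent rule also partly protects the comparison. It obtains tissue after clearance and ties it to an earlier lesional position. If it refers to the lesion previously sampled, it already follows that lesion; if it requires every lesion to have cleared, it does not, and the wording allows both. Similarly, the table's column heading could mean the area that was lesional. It is therefore not a plain contradiction with a resolved condition, but it still gives no location in psoriasis.

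Finally, these are preliminary endpoints, and photographs may let lesion status be partly reconstructed. That help is uncertain at the mid biopsy: the table shows no photograph at Visit 7, while the cohort paragraphs photograph at each session.

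These points limit the scope and weight of the concern. They do not supply a rule for which lesion is sampled, or a resolved-lesion rule for psoriasis.

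**Conclusion.** The concern holds in a conditional form. Followed as written, the plan lets the mid and final biopsies, at most 40 of 60, be selected on response, and it treats resolved lesions differently in the two cohorts. Exposure is greatest where the site holds several lesions, as is likely in Grover's disease, and smallest in a single plaque.

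Neither the size nor the net direction of the bias can be derived. It would be wrong to conclude that the histology will overstate benefit, or that it will understate it. The conclusion also assumes that the biorepository protocol has no rule settling the matter.

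The session-count mismatch is a minor reconciliation. The timing difference is a matter of interpretation: mid-to-final change combines further sessions with a shift from at least 23 hours after light to within the same visit. A reader might say that the final interval is left wholly open, but the table bounds it within Visit 15.

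The point is worth settling before enrolment because the choice of tissue cannot be corrected afterwards.

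**What to change.** - At Visit 1, mark on the baseline photograph three lesions, or three points of one plaque, within the treated site. Assign them at random to the baseline, mid and final biopsies.
- In both cohorts, sample the assigned point whether or not it has cleared, including at early completion, in place of the adjacent rule. State a minimum separation from earlier punches; the geometric floor for two 6 mm punches not to overlap is 3 + 3 = 6 mm centre to centre. Give a fallback for sites that cannot hold three points.
- Record lesion status and sessions received at each biopsy, and report counts by lesion status.
- State how early-completion biopsies enter the count at completion of 15 sessions.
- Reconcile the mid-biopsy timing between the general procedure and the cohort paragraphs, and note the different time since light when interpreting mid-to-final change.
- If the biorepository protocol already holds a site rule, cite it and check that it does not depend on response.

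The cost is a marked photograph, a random order, a few recorded fields and some protocol wording, with no extra biopsies. Small sites may need the fallback. Following lesions from baseline also captures natural resolution: the Background section notes that some Grover's eruptions last two to four weeks, against a five-week course. A fall in counts therefore still could not be attributed to light alone in this single-arm study.
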